# 2.0 Scientific Endpoints

2.1 Describe the scientific endpoint(s), the main result or occurrence under study.

*NOTE:* Scientific endpoints are outcomes defined before the study begins to determine whether the objectives of the study have been met and to draw conclusions from the data. Include primary and secondary endpoints. Some example endpoints are: reduction of

symptoms, improvement in quality of life, or survival. Your response should **not** be a date.

Response:

The **primary** study outcome will be the duration of metabolic acidosis after hospital admission.

Resolution of metabolic acidosis will be defined in three ways to delineate the iatrogenic effect from intravenous fluids from that of the primary pathology in diabetic ketoacidosis:

- 1. Serum ketone level <1mmol/L;
- 2. Venous pH > 7.3;
- 3. Serum bicarbonate level > 15mmol/L.

**Secondary outcomes**: Length of stay in the pediatric intensive care unit and length of stay in the hospital.

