After admission to the PICU, DKA fluid management uses a two-bag system to maintain glucose levels between 100 and 300 mg/dL. Once the patient's glucose concentration falls below 300 mg/dL, the intravenous fluids containing dextrose are started and the fluids without dextrose are titrated downward. In addition to containing necessary electrolytes, the study intravenous fluids will contain either lactated ringer's or normal saline based on the assigned treatment arm.

Study fluid management of the two-bag system will follow the same guidelines for rate of fluid delivery and amount of dextrose used currently in the routine management of patients in DKA. Bedside healthcare personnel will treat all study subjects identically regardless of treatment arm. To provide blinding to all bedside staff, intravenous fluid bags will be labelled as "DKA study fluid with dextrose" or "DKA study fluid without dextrose." The fluid bags will be covered with an opaque black bag to mask any visible description of the fluid content.

Fluids will be adjusted using the study protocol as outlined here:

Serum Glucose	DKA study fluids without dextrose	DKA study fluids with dextrose	
>300mg/dL	100% of the hourly rate	0%	

200-300 mg/dL	50% of the hourly rate	50% of the hourly rate	
<200 mg/dL	0%	100% of the hourly rate	

Study participants will not receive any additional laboratory tests other than those that are already involved in standard DKA management. Currently, routine DKA management involves hourly finger-stick or laboratory glucose levels, every 2-hour serum electrolytes and blood gases, every 6-hour serum beta-hydroxybutyrate levels, and urine ketones with every void. This will be the same for all study participants on both treatment arms.

The study fluids will be used until the acute management of DKA using the continuous insulin infusion and two-bag fluid system is stopped. This will occur when the venous pH is equal to or greater than 7.30, the serum bicarbonate level is equal to or greater than 15 mmol/L and serum ketone levels are less than 1mmol/L.

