#### Response:

Baseline demographic data that will be collected including age, sex, race, comorbid conditions, vital signs, number of hospitalizations for DKA in the preceding 12 months, and date and time of transfer to the PICU.

ED lab data that will be collected include all laboratories obtained in the ED, intravenous fluid volume and type administered, time to start of insulin and PRISM score.

PICU lab data that will be collected include all pH, bicarbonate, anion gap, chloride and beta-hydroxybutyrate levels, sodium, potassium, BUN, creatinine, glucose etc. If the patient remains in DKA after 32 hours after initial ED labs, PICU lab data will be collected until the closest to 36 hours after the initial ED labs were obtained.

Outcomes to be collected include length of stay in the hospital and ICU, resolution of acidosis including time to a serum pH>7.30, bicarbonate >15mg/dl, and normal anion gap.

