#### Response:

Univariate analysis will be used to determine if the subjects in each treatment arm differ at baseline through t-test or Wilcoxon Rank Sum testing for continuous data and Chi-square testing for categorical data. Any differences will be controlled for in the analysis of the primary outcome (length of acidosis) using linear regression. All outcomes will be correlated with the overall chloride load given via intravenous fluids during DKA management. All analyses will be performed using IBM SPSS software, version 25 (Chicago, IL) and SAS (SAS Institute Inc., Cary, NC) with significance set at p<0.05.

17.2 If applicable, provide a power analysis.

*NOTE:* This may not apply to certain types of studies, including chart/records reviews, survey studies, or observational studies. This question is asked to elicit

whether the investigator has an adequate sample size to achieve the study objectives and justify a conclusion.

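### The 36-hour limit on lab abstraction leaves ketone resolution uncaptured in late resolvers, conflicts with the uncapped pH and bicarbonate outcomes, and has no matching rule in the analysis

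*Combined protocol and SAP*

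**What the plan says.** Section 2.1 states that the "study outcome will be the duration of metabolic acidosis after hospital admission". Resolution is defined in three ways: "Serum ketone level <1mmol/L", venous pH above 7.3, and serum bicarbonate above 15 mmol/L.

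Section 10.1 sets no time limit on treatment: "The study fluids will be used until the acute management of DKA using the continuous insulin infusion and two-bag fluid system is stopped". That point is reached when pH, bicarbonate and ketone thresholds are all met. Routine monitoring until then includes "every 2-hour serum electrolytes and blood gases, every 6-hour serum beta-hydroxybutyrate levels". Data come from the electronic medical record (10.4), and participation runs to hospital discharge (11.2).

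Section 10.2 has two adjacent paragraphs that bear on the endpoint:

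- **PICU labs.** These include pH, bicarbonate and beta-hydroxybutyrate. For a child still in DKA after 32 hours, "PICU lab data will be collected until the closest to 36 hours after the initial ED labs were obtained".
- **Outcomes.** The list covers "resolution of acidosis including time to a serum pH>7.30, bicarbonate >15mg/dl, and normal anion gap". No time limit is given, and ketones are not named.

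Section 17.1 adjusts the "primary outcome (length of acidosis) using linear regression". Neither 17.1 nor 17.2 says how to handle a child whose resolution time is not in the dataset.

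**The concern.** The limit applies only to children whose primary endpoint may not yet have occurred. Their later results are in the chart, but the lab-collection rule says to stop reading it. Linear regression needs a completed duration for every child. Someone would therefore have to choose between dropping the child, entering about 36 h, or going back to the record, and that choice could be made after data have been seen.

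If the primary hypothesis is true and saline prolongs acidosis, late resolvers fall mostly in the saline arm. Dropping or capping them in a comparison of means then understates the effect. The children affected are those with prolonged acidosis, the problem that section 3.1 gives as the reason for the trial.

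**Working it through.** **1. What is captured after about 36 h, by definition**

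| Definition (2.1) | In capped lab series (10.2) | In uncapped outcome list (10.2) | Result for a late resolver |
|---|---|---|---|
| Ketones < 1 mmol/L | yes | no | not captured as written |
| pH > 7.3 | yes | yes | paragraphs conflict |
| Bicarbonate > 15 | yes | yes | paragraphs conflict |

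Ketones are measured every 6 h, so the value closest to 36 h may itself lie up to 6/2 = 3 h away. The lab clock starts at the initial ED labs and the endpoint clock at hospital admission, so the observable window on the endpoint clock need not be exactly 36 h.

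**2. Inputs for the size**

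Section 17.2 gives a median of 8 h to anion-gap closure and a further 8 h to resolution. I take 8 + 8 = 16 h as the saline median (adding medians is an approximation). The planned 8 h difference gives a lactated Ringer's median of 8 h. The printed quartiles are unclear, so I use two assumed SDs:

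- Reading the second pair as 3-14 h: SD = (14 − 3)/1.349 = 8.15 h.
- The SD implied by the planned size, from n per arm = 2(z₀.₉₉₅ + z₀.₈₀)²SD²/8². With 2.576 + 0.842 = 3.417 and n = 52, SD = 8 × √(52/23.36) = 11.94 h.

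The plan's own figure does not reproduce from the first SD: 23.36 × (8.15/8)² = 24.3, so 25 per arm and 50 in total, against 104. Section 17.2 gives no SD, test or sidedness, so this does not show 104 to be wrong, and nothing here depends on it. It is the reason for using both SDs.

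**3. Share of children beyond 36 h**

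- Normal: P = 1 − Φ((36 − median)/SD). Saline: 20/8.15 = 2.45 gives 0.7%; 20/11.94 = 1.68 gives 4.7%.
- Lognormal: P = 1 − Φ(ln(36/median)/σ), with σ set so that the SD matches. Saline: 0.811/0.440 = 1.84 gives 3.3%; 0.811/0.579 = 1.40 gives 8.1%.

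Across these cases the saline share is 0.7-8.1% (about 0-4 of 52), and the lactated Ringer's share is 0-3.9% (about 0-2 of 52).

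**4. Effect on the mean difference (hours)**

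| Shape | SD | True | Entered at 36 h | Dropped |
|---|---|---|---|---|
| Normal | 8.15 | 7.4 | 7.4 (−0.2%) | 7.2 (−2%) |
| Lognormal, equal SD | 8.15 | 7.4 | 7.3 (−0.7%) | 7.1 (−4%) |
| Lognormal, equal σ | 8.15 | 8.8 | 8.6 (−3%) | 8.0 (−10%) |
| Normal | 11.94 | 6.7 | 6.5 (−3%) | 5.8 (−14%) |
| Lognormal, equal SD | 11.94 | 7.4 | 7.1 (−4%) | 6.5 (−12%) |
| Lognormal, equal σ | 11.94 | 9.5 | 8.5 (−10%) | 7.1 (−26%) |

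The difference in medians does not change if late children are entered at 36 h. It falls by about 0.1-0.9 h if they are dropped.

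**5. Sensitivity**

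- A 30 h window on the endpoint clock, same medians: 4-14% of saline children exceed it. The loss is 2-16% if capped and 9-36% if dropped.
- Slower resolution (assumed medians 24 h and 16 h, SD 11.94, 36 h limit): 16-17% of saline children exceed it. The loss is 10-18% if capped and 22-39% if dropped.

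**The case against.** The strongest reply is that the limit governs only the serial PICU lab series. Section 10.3 lists a separate outcomes form and PICU laboratory form, the outcome paragraph carries no time limit, and 20.3 continues outcome collection to discharge even after withdrawal. On that reading, pH and bicarbonate times are recorded whenever they occur. This is plausible, and the forms are not available to test it. A reader might infer from the limit that late durations are never observed; the documents do not support that for pH and bicarbonate. For ketones the reply is weaker. The outcome list is worded as inclusive rather than exhaustive, but it names the anion gap, which is not a primary definition, and omits ketones, which are. Nothing exempts ketones from the limit.

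A reader might also infer that the treatment difference is necessarily biased toward zero. It is not. The bias needs a true difference and either dropping late children or capping them in a comparison of means. There is none under no true difference. Nor does capping alter a comparison of medians while fewer than half of each arm exceed the limit, and 17.2 frames the planned effect in medians. The method named in 17.1, however, is linear regression, so the comparison of means is the relevant case.

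Finally, a much larger loss is tempting. Summing the printed quartiles to 7-22 h gives σ = ln(22/7)/1.349 = 0.849. Centred on 16 h, that lognormal puts 17% of saline children beyond 36 h, and 11.5 h becomes 7.7 h (capped, −32%) or 5.2 h (dropped, −55%). But its upper quartile is about 28 h, well above the 22 h it was built from, so the tail is inflated. A lognormal with median 16 h and upper quartile 22 h has σ = ln(22/16)/0.6745 = 0.472. It puts 4.3% beyond 36 h and loses 4% (capped) or 13% (dropped).

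**Conclusion.** The concern holds in a limited form. As written, the collection rule does not capture ketone resolution in late resolvers, gives two conflicting instructions for pH and bicarbonate, and feeds an analysis with no rule for an uncompleted duration. The size is probably small to moderate. It rests on assumed medians of 16 h and 8 h, assumed SDs of 8.15-11.94 h and assumed distribution shapes; a shorter effective window or slower resolution would raise it. The values remain in the chart and can be recovered, so this should be fixed but does not threaten the trial. Confidence is moderate, because the quartiles in 17.2 are unclear and the data forms cannot be seen.

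**What to change.** **Section 10.2.** Replace the 36-hour limit with abstraction of pH, bicarbonate and beta-hydroxybutyrate from the record until each criterion in 2.1 is met or until hospital discharge. Add time to serum ketones below 1 mmol/L to the outcome list, so that the lab and outcome paragraphs agree.

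**Section 17.1.** State that a child discharged or withdrawn before a criterion is met is censored at the last available lab, and use a time-to-event method for the primary comparison. Such children are neither dropped nor entered at 36 h.

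**Cost.** A short amendment, a few more chart values for a small number of children, and slightly more analysis work. No extra blood draws are needed, because 10.1 already treats these labs as routine care. With abstraction to resolution or discharge, the 36-hour limit censors no one and its bias is zero.

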10.3 List any instruments or measurement tools used to collect data
(e.g. questionnaire, interview guide, validated instrument, data collection form).

Include copies of these documents with your submission.

# Response:

Please find the attached (1) Demographic data form, (2) ER laboratory data form, (3) Outcomes data form, (4) PICU laboratory data form, (5) Screening form

10.4 Describe any source records that will be used to collect data about subjects (e.g. school records, electronic medical records).

#### Response:

All the data will be collected from the electronic medical records of enrolled subjects using the Kaleida Health Powerchart system.

10.5 Indicate whether or not **individual** subject results, such as results of investigational diagnostic tests, genetic tests, or incidental findings will be shared with subjects or others (e.g., the subject's primary care physician) and if so, describe how these will be shared.

#### Response:

No individual subject results will be shared with subjects or his or her primary care physician.

10.6 Indicate whether or not **study** results will be shared with subjects or others, and if so, describe how these will be shared.

#### Response:

No study results will be shared with subjects or others. Final results of this study may be presented at a conference or published in a peer-reviewed journal, but only group data will be published in these circumstances; no individual data will be shared.

# **11.0** Study Timelines

11.1 Describe the anticipated duration needed to enroll all study subjects.

Response:

The study will enroll children with DKA for an estimated period of 2 years or as long as needed to reach the target study size of 104 patients. If the number is reached in earlier than anticipated time-period, the enrollment will stop.

11.2 Describe the duration of an individual subject's participation in the study. Include length of study visits, and overall study follow-up time.

#### Response:

Study participation begins from randomization to hospital discharge. The study intervention will cease once acute DKA management is stopped in the PICU prior to floor transfer. The choice of intravenous fluid, if any needed, will then be left to the discretion of the managing team.

11.3 Describe the estimated duration for the investigators to complete this study (i.e. all data is collected and all analyses have been completed).

#### Response:

We plan to complete patient recruitment with 2 years of time based on the volume seen in a previously completed chart review study. With an additional 6 to 9

months needed for data analysis and manuscript preparation, a total of 33 months will span study initiation to completion.

# 12.0 Setting

12.1 Describe all facilities/sites where you will be conducting research procedures. Include a description of the security and privacy of the facilities (e.g. locked facility, limited access, privacy barriers). Facility, department, and type of room are relevant. Do not abbreviate facility names.

NOTE: Examples of acceptable response may be: "A classroom setting in the Department of Psychology equipped with a computer with relevant survey administration software," "The angiogram suite at Buffalo General Medical Center, a fully accredited tertiary care institution within New York State with badge access," or, "Community Center meeting hall."

#### Response:

This study will be performed in the private patient's room in Emergency Department and the Pediatric Intensive Care Unit of John R Oishei Children's Hospital. It is a fully accredited, free-standing children's hospital with academic and tertiary care services.

12.2 For research conducted outside of UB and its affiliates, describe:

- Site-specific regulations or customs affecting the research
- Local scientific and ethical review structure

NOTE: This question is referring to UB affiliated research taking place outside UB, i.e. research conducted in the community, school-based research, international research, etc. It is not referring to multi-site research. UB affiliated institutions include Kaleida Health, ECMC, and Roswell Park Cancer Institute.

Response:

 $\boxtimes$  N/A: This study is not conducted outside of UB or its affiliates.

# **13.0** Community-Based Participatory Research

*13.1 Describe involvement of the community in the design and conduct of the research.* 

NOTE: Community-Based Participatory Research (CBPR) is a collaborative approach to research that equitably involves all partners in the research process and recognizes the unique strengths that each brings. CBPR begins with a research topic of importance to the community, has the aim of combining knowledge with action and achieving social change to improve health outcomes and eliminate health disparities.

#### Response:

 $\boxtimes$  N/A: This study does not utilize CBPR.

*13.2* Describe the composition and involvement of a community advisory board.

Response:

 $\boxtimes$  N/A: This study does not have a community advisory board.

#### Describe other resources available to conduct the research.

Response: A group of research assistants in the ED will help us to screen potential eligible patients seven days a week.

14.2 Describe the time and effort that the Principal Investigator and research staff will devote to conducting and completing the research.

*NOTE: Examples include the percentage of Full Time Equivalents (FTE), hours per week. The question will elicit whether there are appropriate resources to conduct the research.* 

Response:

The study PIs will share the duties of study maintenance, surveillance and data collection. This could represent upwards of 5-10 hours per week depending on study enrollment volume.

The PI, [name], will be offsite for one year starting in July 2019. [name] will be responsible for daily supervision of the project while she is gone. This is estimated to represent 2-3 hours per week over the course of the project.

14.3 Describe the availability of medical or psychological resources that subjects might need as a result of anticipated consequences of the human research, if applicable.

*NOTE:* One example includes: on-call availability of a counselor or psychologist for a study that screens subjects for depression.

#### Response:

There is no need for medical or psychological resources for subjects of this project, since this study involves no more than minimal risk. Patients enrolled in this study will receive either normal saline or lactated ringer intravenous fluids; both of which are used by physicians per clinical discretion as a part of routine DKA care. Being in the study does not add extra risk for subjects.

14.4 Describe your process to ensure that all persons assisting with the research are adequately informed about the protocol, the research procedures, and their duties and functions.

Response:

The PI, co-PIs, and study coordinator have been involved in the study protocol development. They know the study aims, design, and procedures very well. The PI will train the co-PIs on data collection prior to subject enrollment.

In addition, the PI and co-PIs will present the study at the PICU and ED faculty and research meetings to inform them of the study protocol and procedures, to ensure compliance and update on changes. For those who miss the training at the faculty meetings, the PI and co-PI will offer individual training to them. In addition, the PI, co-PI or the study coordinator will offer training to the PICU and ED fellows on how to obtain consent. The refresh training will be done every 12 months or when new personnel start in each division. All the training procedures will be documented on the training log as part of regulatory documents.

Our research assistants (RA) in the ED are directly working under the supervision of the study coordinator. The RAs' job duties include: screening potential eligible patients and assisting subject enrollment. The study coordinator will provide training to all RAs before the start of recruitment. In addition, RA re-training will be done every 12 months during the subject recruitment period. All training process will be documented on training logs.

The training will focus on the following aspects:

1. Review study protocol by presenting the materials to the RAs with a slide show. The RAs are required to understand the study aims/purpose and the detail study procedures.

2. Review subject screening form. The RAs are required to know the inclusion and exclusion criteria for the study and know what kind of patients are potentially eligible and need to screen for the study.

3. Training the RAs on the post consenting procedures including sending the consent to pharmacy, and transferring the fluid bag back to the ED.

The trainer and trainees' names will be documented in the training log. The training log will be kept as one of the regulatory documents for this study.

All our study team members are CITI trained.

# **15.0 Other Approvals**

15.1 Describe any approvals that will be obtained prior to commencing the research (e.g., school, external site, funding agency, laboratory, radiation safety, or biosafety).

Response:

 $\boxtimes$  N/A: This study does not require any other approvals.

# **16.0 Provisions to Protect the Privacy Interests of Subjects**

16.1 Describe how you will protect subjects' privacy interests during the course of this research.

*NOTE: Privacy refers to an individual's right to control access to him or herself. Privacy applies to the person. Confidentiality refers to how data collected about individuals for the research will be protected by the researcher from release. Confidentiality applies to the data.* 

Examples of appropriate responses include: "participant only meets with a study coordinator in a classroom setting where no one can overhear", or "the participant is reminded that they are free to refuse to answer any questions that they do not feel comfortable answering."

#### Response:

The study team will approach patients and their legal guardians in the private patient rooms in the ED or PICU to introduce the study to them when no other people are around.

16.2 Indicate how the research team is permitted to access any sources of information about the subjects.

*NOTE:* Examples of appropriate responses include: school permission for review of records, consent of the subject, HIPAA waiver. This question **does apply** to records reviews.

